1.2 Importance of a Non-HPV-Specific LA-HNSCC Trial

A recently published retrospective analysis of oropharyngeal cancer patients from RTOG 0129 identified factors associated with prognosis (survival outcome) [Ang 2010]. Tumor HPV status, as determined by expression of p16, was a strong independent predictor of survival. p16 positive patients had the most favorable survival outcome (3-year OS rates of 82.4%), while p16 negative patients had the worse outcome (3-year survival rates of 57.1%). An intermediate prognostic group also was identified that was p16 positive but had a significant smoking history. Implicit from this analysis is that p16 negative (non-HPV) oropharyngeal cancer patients behave much like the p16 negative, non-oropharyngeal, head and neck cancer population. Epidemiologic studies indicate that HPV positive population is a growing subset of HNSCC (Sturgis 2007). Nonetheless, the non-HPV population still represents the majority of HNSCC cases. It can be estimated that roughly 75% of non-HPV HNSCC cases will have aberrant p16, and therefore, carry a poor prognosis (Reed 1996; Gruttgen 2001; Bova 1999).

A clinical trial specifically designed for this poor prognostic population has not been conducted in the cooperative oncology group setting but is appropriate for several reasons. First, the molecular pathogenesis of disease of this group is quite distinct from the HPV population. In HPV-related oropharyngeal HNSCC, expression of viral E6 and E7 oncoproteins that inactivate p53 and pRb is the known mechanism of carcinogenesis (Rampias 2009). In contrast, non-HPV HNSCC is thought to occur as a result of a cumulative multistep process of genetic and epigenetic events due to chronic exposure to environmental carcinogens. Second, cooperative group oncology clinical trials specifically designed for HPV oropharyngeal cancer are active. Finally, the prognosis is unacceptably poor for this non-HPV HNSCC population; significant effort is necessary in order to improve their outcome. For all these reasons, a specific study for HPV negative patients is necessary in order to make overall progress in the treatment of HNSCC.

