11.5 Quality of Life/Patient-Reported Outcomes Instruments

Note: Patients must be offered the opportunity to participate in the correlative components of the study, such as quality of life assessment. If the patient consents to participate in the quality of life (QOL) component of the study, sites are required to administer the baseline QOL and PRO assessments prior to the start of protocol treatment: the PSS-HN, FACT-HN, and XEQOLS. Outcomes will be assessed at baseline (pretreatment) and at 3, 12, and 24 months from completion of radiation treatment.

- #### **11.5.1 *The Functional Assessment of Cancer Therapy-Head & Neck (FACT-H&N)*** is a multidimensional, patient-self report quality of life (QOL) instrument specifically designed and validated for use with head and neck patients. The patient can complete the 12-item head and neck subscale in 5-10 minutes. The site research nurse or CRA is encouraged to be sensitive to each patient's demeanor. If patients appear particularly uncomfortable answering a question, they will be informed that they can skip that question. Similarly, interviewers will give patients a short break if the patient appears fatigued or otherwise in need of a few minutes break.

- 11.5.2** *The University of Michigan Xerostomia-Related Quality of Life Scale (XeQOLS)* consists of 15 items covering 4 major domains of oral health-related quality of life: physical functioning, personal/psychological functioning, social functioning, and pain/discomfort issues. The patient can respond to the 15 items in the scale in approximately 5 minutes. The Scale is only available in English.
- 11.5.3** *The Performance Status Scale for Head and Neck Cancer (PSS-HN)* consists of assessment of 3 functional areas (subscales): Normalcy of Diet, Eating in Public, and Understandability of Speech. The site research nurse or clinical research associate (CRA) will administer the PSS-HN. Interviewers are encouraged to be sensitive to each patient's demeanor. If patients appear particularly uncomfortable answering a question, they will be informed that they can skip that question. Similarly, interviewers will give patients a short break if the patient appears fatigued or otherwise in need of a few minutes break. The interviewer rates the patient on each scale based on the patient's responses to targeted questions. The PSS-HN takes approximately 5 minutes to complete.

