13.3 Randomization and Stratification (10/3/13)

Patients will be randomized to 1 of 2 treatment arms. Additionally, patients will be stratified according to age (≤ 65 vs. > 65); T stage (T1-3 vs. T4); and N stage (N0-2a vs. N2b-3).

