13.6 Analysis Plan (9/27/16)

Progression-free and overall survival rates will be estimated using the Kaplan-Meier method (1958) and rates of distant metastasis (DM) and local-regional control (LRC) by the cumulative incidence method (Kalbfleisch 1980) to account for competing risks (see Section 13.4). The distributions of the progression-free and overall survival times will be compared between treatment arms with a one sided log rank test (Mantel, 1966). Distant metastasis and local-regional control will be compared using cause-specific log rank test. If the resulting p-value for PFS is < 0.1803 , the result will be interpreted as a significant indication of lapatinib improving progression-free survival of these patients to warrant a definitive phase III trial.

Only adverse events (AEs) assessed to be definitely, probably, or possibly related (if the relationship is missing, it will be assumed to be definitely, probably, or possibly) to protocol treatment will be considered. The rates of adverse events and treatment compliance will be estimated using a binomial distribution along with their associated 95% confidence intervals and will be compared using Fisher's exact test.

Comparison of change from baseline quality of life scores between the 2 arms will be done using a 2-sample independent t test. With 158 patients, we will have 87% power to detect an effect size of 0.5 with a two-sided type I error rate of 5% and the statistical power will be 79% and 66% to detect effect sizes of 0.5 with 126 and 94 patients. Analysis of the covariance model (ANCOVA) will be used to adjust for effects from other factors.

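### The named quality-of-life comparison is an unadjusted change-score t test; the ANCOVA beside it does not name the baseline score, and no visit is fixed for either

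*Combined protocol and SAP*

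**What the plan says.** Section 13.6 gives QOL one short paragraph. The comparison is stated as: "Comparison of change from baseline quality of life scores between the 2 arms will be done using a 2-sample independent t test". Power is then given for that comparison: "With 158 patients, we will have 87% power to detect an effect size of 0.5 with a two-sided type I error rate of 5"%. For smaller numbers the plan adds: "statistical power will be 79% and 66% to detect effect sizes of 0.5 with 126 and 94 patients". The paragraph closes with: "Analysis of the covariance model (ANCOVA) will be used to adjust for effects from other factors". It lists no covariates and does not say whether the t test or the ANCOVA carries the conclusion.

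Section 11.5 schedules the instruments before treatment and at "3, 12, and 24 months from completion of radiation treatment". Section 13.6 ties the test to none of these visits. Section 1.5 does name one: it expects less favourable scores with lapatinib at 3 months after radiation. The same section calls the QOL work exploratory and says its goal is to supply means and standard deviations for sizing a later phase III trial. Section 13.2 lists QOL as a secondary endpoint, and participation needs separate consent. Neither section says how scores missing through death, dropout or an unreturned form are handled.

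**The concern.** A t test on change subtracts the baseline score with a coefficient fixed at 1. ANCOVA estimates that coefficient. Unless the true slope of follow-up on baseline happens to be 1, the fixed subtraction leaves avoidable noise, and it over- or under-corrects when the arms differ by chance at baseline. The baseline score is collected in every QOL participant, so this precision is available at no cost.

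The wording also leaves choices open. An ANCOVA with unnamed covariates, an undefined rank against the t test and no stated visit allows several analyses of three instruments at three follow-up visits, any of which could be called the planned one. The component exists to produce effect sizes that a phase III design will reuse, so imprecise or loosely defined estimates would carry forward.

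**Working it through.** **Inputs from the documents.** Effect size 0.5 and two-sided 5% error (Section 13.6); 158, 126 and 94 patients with stated power 87%, 79% and 66% (Section 13.6); 128 analysable patients under the revised plan (Section 13.5). Section 13.3 says only "Patients will be randomized to 1 of 2 treatment arms"; I assume 1:1.

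**Assumed, because the documents do not give them.** The baseline/follow-up correlation r (range 0.3 to 0.7), the ratio k of follow-up SD to baseline SD, and the reading of 0.5 as a multiple of the SD of change.

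**Step 1: reproduce the plan.** For a two-sample t test with N/2 per arm, the noncentrality is d × √(N/4) with N − 2 degrees of freedom.

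| N | Noncentrality | Power | Plan |
|---|---|---|---|
| 158 | 0.5 × √39.5 = 3.14 | 87.8% | 87% |
| 126 | 0.5 × √31.5 = 2.81 | 79.5% | 79% |
| 94 | 0.5 × √23.5 = 2.42 | 67.0% | 66% |

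The plan's figures reproduce to within about one point for the unadjusted two-sided test, so that is the test the plan is powered on. At the current 128 patients the same calculation gives 0.5 × √32 = 2.83 and power 80.2%.

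**Step 2: variance with baseline adjustment.** Take the baseline SD as 1 and the follow-up SD as k.
- Variance of change: 1 + k² − 2rk.
- Residual variance after regression on baseline: k²(1 − r²).
- Ratio, ANCOVA to change score: V = k²(1 − r²) / (1 + k² − 2rk).
- With k = 1 this is (1 − r²) / (2 − 2r) = (1 + r)/2.
- The difference between the two variances, change minus ANCOVA, is (1 − rk)². This is never negative, so in large samples adjustment cannot be less precise.

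**Step 3: power at N = 128.** The effective effect size is 0.5/√V. The one degree of freedom spent on the covariate is ignored.

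| k | V at r = 0.3 / 0.5 / 0.7 | Power at r = 0.3 / 0.5 / 0.7 |
|---|---|---|
| 1 | 0.65 / 0.75 / 0.85 | 93.6% / 90.0% / 86.1% |
| 1.5 | 0.871 / 0.964 / 0.998 | 85.3% / 81.6% / 80.2% |
| 0.8 | 0.502 / 0.571 / 0.628 | 97.7% / 96.0% / 94.3% |

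All compare with 80.2% for the t test. With equal spread the gain is 6 to 13 points. With a follow-up SD 1.5 times baseline it is 0 to 5 points. It is larger if the spread narrows.

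**Step 4: other reading of the effect size.** If 0.5 means SDs of the raw score, with k = 1 and N = 128, the t test has 66.0% / 80.2% / 95.2% power at r = 0.3 / 0.5 / 0.7, against 83.7% / 90.0% / 97.6% for ANCOVA. The direction is the same.

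**Step 5: chance imbalance.** If the arms differ by δ at baseline, the expected change-score difference is shifted by (rk − 1)δ. ANCOVA estimates the slope rk and removes the shift.

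**The case against.** Several points on the other side are sound. In a randomised trial the change-score t test is valid and unbiased on average, so the issue is precision. The plan does include an ANCOVA, and its phrase "will be used to adjust for effects from other factors" neither names nor rules out the baseline score. A reader might infer that the plan refuses to adjust for baseline. The text does not support that; it supports only that the covariates and the role of the ANCOVA are unspecified.

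A reader might also infer separate complete-case tests at 12 and 24 months, and go on to compute power among 24-month survivors from the "3-year survival rates of 57.1"% quoted in Section 1.2. That goes beyond the documents. Section 13.6 names no visit and the only stated hypothesis is at 3 months. The survival figure comes from p16-negative oropharynx patients in an earlier trial, whereas this trial also enrols larynx and hypopharynx. A 24-month value would further need an assumed hazard shape.

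Nor is reduced power at lower numbers hidden. The plan gives it at 126 and 94 patients, about 80% and 60% of 158. The documents do not explain those numbers, but they fit an allowance for lost forms.

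Finally, a repeated-measures model adds little at 3 months, the first follow-up visit, and no such model cures selection by death. This limits the remedy at later visits. It does not answer the case for baseline adjustment at 3 months.

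**Conclusion.** The point holds in a limited form. The comparison that Section 13.6 names and powers is an unadjusted t test on change. The ANCOVA is not specified to adjust for the baseline score or to take precedence, and the 3-month hypothesis is not linked to an analysis. Baseline-adjusted ANCOVA is the better main analysis on data already being collected.

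The gain at 128 patients runs from almost nothing to about 13 points of power when the follow-up spread is equal to or wider than baseline, and more if it narrows. These figures assume 1:1 allocation, an effect of 0.5 SD of change, and scores from all 128. Because participation is optional, the number with scores may be lower. No single power gain should be quoted as established, since the documents give neither the correlation nor the SDs.

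The consequence is the precision and clarity of secondary, exploratory estimates meant for phase III planning. The primary progression-free survival conclusion does not depend on it.

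**What to change.** In Section 13.6:

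- Make ANCOVA of the 3-month score the main QOL comparison, with treatment, the baseline score and the stratification factors (age, T stage, N stage) as covariates. Keep the change-score t test, if wanted, as supportive.
- Analyse 12 and 24 months with a repeated-measures model that includes the baseline score.
- Report the numbers alive and the numbers assessed, by arm, at each visit. Describe the later results as applying to survivors, under a missing-at-random assumption for absent forms.
- Report the baseline/follow-up correlation and the SD at each visit, which a phase III design will need.
- Restate the power sentence, whose largest figure is still 158, for the 128 analysable patients.

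The cost is SAP wording and slightly more analysis work, with no new data or visits. The limits remain: the missing-at-random assumption cannot be verified, and the model does not define quality of life after death.

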- 10.0 Tissue/Specimen Submission
- 11.0 Patient Assessments
- 12.0 Data Collection
- 13.0 Statistical Considerations

References

- Appendix I - Study Parameters
- Appendix II - Performance Status Scoring
- Appendix III - Staging System
- Appendix IV - Biospecimen Collection Instructions
- Appendix V - Diarrhea Management
- Appendix VI - Prohibited Medications
- Appendix VII - Dental Management

RTOG FOUNDATION STUDY 3501

TryHard: A Phase II, Randomized, Double Blind, Placebo-Controlled Study of Lapatinib (Tykerb®) for Non-HPV Locally Advanced Head and Neck Cancer with Concurrent Chemoradiation

SCHEMA (9/27/16)

			Age		
R		S	1. ≤ 65	R	Week 1: lapatinib/placebo
E	*For	T	2. > 65	A	
G	oropharyngeal	R		N	Weeks 2-7: AFX RT + cisplatin
I	cancer	A	T Stage	D	+ lapatinib/placebo
S	patients:	T	1. T1-3	O	
T	Mandatory	I	2. T4	M	Followed by maintenance lapatinib/placebo
E	analysis for	F		I	for 3 months
R	p16 status	Y	Nodal Status	Z	
			1. N0-N2a	E	
			2. N2b-N3		

*Oropharyngeal cancer patients must be negative for p16, prior to Step 2 registration (randomization); these patients must consent to use of the submitted tissue for required HPV analysis. Analysis results are expected in approximately 7-10 business days. At that time, patients with oropharyngeal carcinoma can be randomized. See Section 5.3 for details. **Note:** If a specimen was previously submitted to the Biospecimen Bank at UCSF for determination of HPV status for another RTOG trial and found to be p16 negative, investigators can forward a Specimen Transmittal (ST) Form to the Biospecimen Bank at UCSF requesting that the specimen be sent to [name] for central lab confirmation of p16 negativity.

Intensity Modulated Radiation Therapy (IMRT) is mandatory for this study. Image-Guided radiation therapy (IGRT) is mandatory when using a PTV margin of < 5 mm.

Patient Population: (See Section 3.0 for Eligibility)

Pathologically (histologically or cytologically) proven (from primary lesion and/or lymph nodes) diagnosis of Stage III or IV squamous cell carcinoma of the oropharynx, hypopharynx, or larynx; for patients with an oropharynx primary site, the tumor must be negative for p16 by immunohistochemistry.

Required Sample Size: 142

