13.5 Sample Size and Patient Accrual (9/27/16)

This study will be a randomized phase II screening trial as proposed by Rubinstein, et al (2005). Based on the accrual to RTOG 0129 in this population, it is expected that the monthly accrual will be 12 patients after the first 6 months post-activation (allowing for IRB approvals). In RTOG 0129, this group of patients treated on the accelerated fractionation arm had a 2-year progression-free survival (PFS) rate of 53.5%. Hazard rates for first and second years are 37% and 15%. Based on discussions with the study chair, a 35% reduction in the hazard rate is clinically meaningful. With statistical power 0.80 and significance level 0.20 (1-sided) and one interim efficacy and futility analysis, the Lan-Demets (OF) spending function boundary for efficacy and rho family spending function with parameter of 1.5 for futility were utilized to derive a nonbinding rule. A total of 69 PFS events are required. To observe the required number of events, a sample size of 158 accrued over 1.22 years with an additional 2.6 years of follow-up (total study duration 4.3 years including 6 months for IRB approvals) is required. Allowing for up to 10% of patients to be ineligible or not evaluable, **the total original required sample size is 176.**

Following activation of the study little accrual is anticipated initially. The date at which the first patient is accrued will be used as the baseline for monitoring accrual. If the total accrual during months 18 through 24 is less than 20% of the projected total for 6 months of accrual (15 patients), then the study statistician will recommend to the RTOG DMC and the sponsor that the protocol will be discontinued. If the total accrual is between 21-49%, then the protocol will continue to accrue subjects pending approval to remain open by the RTOG DMC and the study sponsor.

Revised Sample Size and Patient Accrual

As of September 2016, the observed accrual rate in this study is about 30 patients/year (2.5/month). To finish accrual within a reasonable timeframe and to maintain the same design parameters detailed above, we plan to accrue a total of 142 patients (128 analyzable), with a total accrual duration of 4.7 years instead of 5.9 years. According to this plan, we will finish accrual around March 2017.

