For analysis of local-regional control, distant metastasis, PFS, and OS, we will examine whether patients with normal baseline levels of biomarkers have a different prognosis than patients with abnormal baseline levels by calculating the product-limit estimates of the survival function and comparing those estimates using the log-rank statistic. The relationship between local-regional control, distant metastasis, PFS, OS, and abnormal baseline marker levels also will be explored by fitting Cox proportional hazards regression models, both adjusted for baseline disease and patient characteristics and unadjusted. Assuming usable baseline tissue/blood samples can be obtained from 118 eligible patients (~75%), this will provide at least modest power (>69%) to detect large differences (hazard ratios > 2.0) between patients with normal and abnormal marker levels, assuming 50% abnormal prevalence, with a two-sided 5% alpha, for the PFS endpoint.

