13.6.4 Analysis for Reporting the Final Treatment Results

The analysis to report the definitive results of treatment will be undertaken when 69 events (total from both arms) have been reported for the primary endpoint, PFS, unless the criteria for early stopping are met. The time from when accrual is finished to this analysis is projected to be approximately 2.7 years based on the observed accrual rate. All randomized patients (ITT) will be included in this analysis. Eligible patients with both on-study and follow-up information will be considered for sensitivity analysis. The usual components of this analysis are:

- Tabulation of all cases entered, and any excluded from analysis with reasons for exclusion;
- Patient accrual rate;
- Institutional accrual;
- Distribution of important baseline prognostic variables;
- Frequency and severity of adverse events;
- Observed results with respect to the endpoints described above.

The difference in PFS between the control arm and the experimental arm will be tested using the one sided log-rank statistic at the significance level of 0.1803 given that the one interim analysis is carried out and shows no statistical significance. If the resulting p-value for efficacy is <0.1803, this result will be interpreted as an indication of lapatinib in improving progression-free survival in these patients.

A final analysis report will be prepared and provided for review by the co-investigators. Results for dissemination will be developed, and a manuscript drafted for review, approval, and submission. After manuscript acceptance, patient follow up will be discontinued and the trial terminated. It is anticipated that termination will occur approximately 3.9 years from when the accrual is finished. This time-frame may be extended depending on factors such as the observed accrual and event rates, in which case a new trial termination date will be established.

REFERENCES

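### The quality-of-life power statement in Section 13.6 still uses 158 patients, although the trial was cut to 142 (128 analyzable): power is about 80% at 128 and at most 84%, not 87%

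*Combined protocol and SAP*

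**What the plan says.** Section 13.5 (9/27/16) first derives 158 evaluable patients, inflated to 176 for ineligible or non-evaluable patients, and calls 176 the original requirement. Under its revised sample size heading it then replaces that plan: "we plan to accrue a total of 142 patients (128 analyzable"). The schema of the same date agrees: "Required Sample Size: 142".

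Section 13.6, also dated 9/27/16, sets out the QOL analysis: "Comparison of change from baseline quality of life scores between the 2 arms will be done using a 2-sample independent t test". Its power statement begins "With 158 patients, we will have 87% power to detect an effect size of 0.5 with a two-sided type I error rate of 5" per cent and goes on: "the statistical power will be 79% and 66% to detect effect sizes of 0.5 with 126 and 94 patients". No power is given for 128 or 142 patients.

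Three other places bear on the point:

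- Section 13.6.4 sets the population for the final analysis: "All randomized patients (ITT) will be included in this analysis".
- Section 11.5 makes QOL participation optional: "If the patient consents to participate in the quality of life (QOL) component of the study", sites must collect the baseline forms. Follow-up forms are due 3, 12 and 24 months after radiation.
- The biomarker paragraph of Section 13.6 reads "Assuming usable baseline tissue/blood samples can be obtained from 118 eligible patients (~75" per cent), and claims more than 69% power for hazard ratios above 2.0 on PFS.

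**The concern.** The sample size was cut in Section 13.5, but the QOL power in Section 13.6 was left on the old evaluable number. Section 13.5 labels its superseded total as original; Section 13.6 carries no such label and reads as the current plan. No consent or completion rate can yield 158 patients from a trial that randomizes 142.

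QOL is a listed secondary endpoint, and Section 1.5 states a directional hypothesis that scores will be worse with lapatinib at 3 months. If no difference is found, a reader will judge that result against the stated 87%, which overstates what the trial could detect.

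The two lower cases may be affected as well. The plan does not say where 126 and 94 come from, but they are close to 80% and 60% of 158. If they are attrition cases, all three figures rest on the old base.

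**Working it through.** **Inputs**

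- Test: two-sample t-test on change from baseline, effect size d = 0.5, two-sided 5% (Section 13.6).
- Patient numbers: 158, 126 and 94 with stated power 87%, 79% and 66% (Section 13.6); 142 accrued and 128 analyzable (Section 13.5).
- Allocation: 1:1 assumed. Section 13.3 names two arms but gives no ratio.

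**Formula.** With N patients in equal arms, the t statistic is noncentral t with N − 2 degrees of freedom and noncentrality d × √(N/4). Power is the probability that its absolute value exceeds the two-sided 5% critical value.

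**Step 1: reproduce the plan's figures**

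| N | Noncentrality | Critical t | Power | Stated |
|---|---|---|---|---|
| 158 | 0.5 × √39.5 = 3.142 | 1.975 | 87.8% | 87% |
| 126 | 0.5 × √31.5 = 2.806 | 1.979 | 79.5% | 79% |
| 94 | 0.5 × √23.5 = 2.424 | 1.986 | 67.0% | 66% |

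All three agree to about one percentage point. The method is right; the patient number is out of date.

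**Step 2: apply the revised numbers**

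| N | Noncentrality | Critical t | Power |
|---|---|---|---|
| 142 | 0.5 × √35.5 = 2.979 | 1.977 | 84.1% |
| 128 | 0.5 × √32 = 2.828 | 1.979 | 80.2% |

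**Step 3: what 87% would need.** N = 154 gives 86.9% and N = 155 gives 87.1%, so about 155 patients with usable change scores are needed, 13 more than will be randomized. Conversely, the effect detectable with 87% power is 0.52 at 142 and 0.55 at 128.

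**Step 4: the lower cases.** 126/158 = 80% and 94/158 = 59%, but 126/128 = 98% and 94/128 = 73% (89% and 66% of 142). The 79% at 126 therefore remains true, but it now describes almost full completion of the analyzable sample. If 80% and 60% completion were meant (an inference), the values for 128 are:

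- 0.80 × 128 ≈ 102 patients: power 70.6%.
- 0.60 × 128 = 76.8 patients: power 57.6% at 76 and 58.1% at 77.

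**Step 5: the biomarker sentence.** 118/158 = 75%, but 118/128 = 92%; 75% of 128 is 96. If events scale with samples, 0.75 × 69 = 51.75 events. For a hazard ratio of 2.0 and 50% prevalence, power is Φ(ln 2 × √51.75 / 2 − 1.96) = Φ(0.533) = 70.3%. The claim of more than 69% survives; only the count and its percentage no longer agree.

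**The case against.** The strongest case is that this is a lapse in updating with little consequence. The same sentence already gives 79% at 126, two patients below the analyzable 128, so a reader who knows the revised size can find the right value to within about one point. The 87% was always a best case, because it required QOL data from all 158 patients, and 80% and 84% lie inside the stated range of 66% to 87%. Section 1.5 calls the QOL component exploratory and aims it at effect-size estimates for phase III. No decision rests on it: the only decision rule is on PFS. Accrual was due to finish around March 2017, and one section of the current text is dated 3/22/17, so the design was essentially fixed. Finally, the completion rates behind 102 and 77 patients are not in the plan, and 118 samples are still attainable from 128 patients.

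Much of this stands. No formula is wrong, the harm is small, and the lower completion cases are illustrations. None of it makes 158 attainable or 87% correct. The 79% figure helps only a reader who already knows that the leading figure should be ignored, and it is no longer a middle case for the analyzable sample. Late timing limits the effect on the design, but the power statement will still be used to read the result.

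**Conclusion.** The concern holds. The leading QOL power figure cannot be achieved under the current plan. The planned t-test has 80.2% power on the 128 analyzable patients and 84.1% if all 142 randomized patients contribute: about 7 and 3 points below the stated 87%, before any loss to non-consent or missing forms.

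These figures assume 1:1 allocation and the plan's own effect size and error rate. The 71% and 58% values rest further on assumed completion of 80% and 60%, which the documents do not give.

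The effect is limited to the power statement. The event-driven PFS design (69 events), the effect-size estimates meant for phase III and the biomarker power claim are not affected.

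**What to change.** In the QOL paragraph of Section 13.6, replace the figures for 158, 126 and 94 patients with 84% at 142 (the maximum, if every randomized patient contributes) and 80% at 128. If lower cases are kept, rebase them on 128 as about 71% at 102 and 58% at 77, labelled as assumed 80% and 60% completion, or use completion rates that the sponsor can support.

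In the biomarker paragraph, make the count and percentage agree: either 96 eligible patients (about 75% of 128), with a note that the power rests on about 52 PFS events, or 118 described as about 92% of 128.

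Optional and separate: name the baseline score as a covariate in the ANCOVA already planned. Any gain in power depends on a baseline-to-follow-up correlation that the documents do not give.

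The cost is wording in two sentences and a less favourable stated QOL power. Data collection, sample size and the primary analysis do not change.
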